In addition to these **Specific Aims**, we will monitor subjects' MA use, as improvements in brain bioenergetics, mood/anxiety and may decrease MA usage. Therefore, we will record urine drug testing results, to determine whether creatine vs. placebo is associated with a greater number of MA-free tests during the 8 weeks of randomized treatment.

PARTICIPANT SELECTION CRITERIA

123 women will be randomly assigned in a 1:1 ratio to either creatine or placebo for eight weeks. Table 1 outlines eligibility criteria.

TABLE 1 INCLUSION AND EXCLUSION CRITERIA

INCLUSION CRITERIA:

- Female gender, ages 18-55 inclusive
- Current primary diagnosis of MA dependence or abuse, with MA preferred drug of abuse (Lifetime MA use > 20 grams)
- Current diagnosis of Major Depressive Disorder (MDD)
- Current HAMD score ≥ 10
- Clinical Global Impressions–Severity (CGI-S) depression score ≥ 4
- If taking a psychotropic medication for depressed mood, regimen must be stable for ≥ 4 weeks prior to randomization

EXCLUSION CRITERIA:

- Persons unable to provide adequate informed consent
- Persons who are at clinically significant suicidal or homicidal risk
- Primary substance-related diagnosis *other than* MA dependence or abuse
- Comorbid substance dependence diagnosis, other than nicotine (substance abuse diagnoses are not excluded)
- Positive pregnancy test, due to the unknown effects of MRI scanning on the unborn fetus
- Positive test for antibody to the Human Immunodeficiency Virus (HIV)
- History of renal disease
- Clinically significant medical or neurological illness identified by history, physical exam and laboratory testing
- Known or suspected intellectual disability, or developmental disorder, e.g. autism
- History of hypersensitivity reaction to creatine

WITHDRAWAL / EARLY TERMINATION CRITERIA:

- Withdrawal of informed consent
- Suicide attempt
- Psychiatric hospitalization
- Onset of bipolar disorder or psychotic disorder
- Positive pregnancy test
- Incarceration
- Inability to comply with study protocol

▪ Treatment with electroconvulsive therapy (ECT)▪ Increase in HAMD score > 25% from baseline▪ Serious adverse event

▪ HEALTHY CONTROL SUBJECTS:
 
▪ Female gender, ages 18-55 inclusive▪ No current or past DSM-5 diagnosis, as determined by clinical and structured interviews▪ No first-degree relatives with known or suspected DSM-5 diagnosis

DESIGN

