The proposed study will use a randomized, double-blind, placebo-controlled design. 123 participants will be randomly assigned in a 1:1 ratio to placebo or 5 grams of daily creatine treatment for eight weeks. We also plan to recruit 24 age-matched females (18-55).

STUDY PROCEDURES

All procedures performed by study personnel are research-related. None of the study activities will be considered standard of care. There will be no cost to study subjects for their participation. Participants will be compensated for their time and travel. Table 2A and 2B outlines the schedule of study procedures for treated participants and healthy controls.

Consent will be obtained before any study procedures are initiated. Potential participants will be informed of the study and offered a consent form to review. They will be encouraged to discuss study participation with their relatives. If a potential participant expresses interest in study participation, the informed consent process will be conducted. After the informed consent process, individuals will be offered time to consider study participation and to ask questions. Subjects and parents/guardians will have the opportunity to discuss the study with a study team member in a setting free of coercion. The language of the informed consent form is written at a level easily understood by the subject and any questions asked by the subject will be answered honestly and free of bias. A specific meeting time will be set up between a study team member and the participant where the entire informed consent document will be carefully explained in its entirety. The length of the meeting will be designed so there is the necessary amount of time for all questions to be answered.

Randomization of participants to the two treatment conditions will take place according to a randomization list generated prior to the start of recruitment. 47 (50%) will be randomized to placebo. The study will be conducted as a double-blind trial, with neither participants nor research staff aware of participant assignment. Except in cases of medical emergency, the double-blind will not be "broken" until recruitment is closed and the final participant has completed 8 weeks of treatment with investigational drug. There is no "washout period" for any participant in this study, and participants randomized to placebo will continue treatment with a psychotropic medication throughout their time in the study.

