- During the intake and assessment interview, participants may become emotionally upset when asked about their psychiatric history including suicide attempts, or physical and sexual abuse.
- There is a 50% chance that the participant will be assigned to placebo, in which they will not receive creatine.
- Participants may experience discomfort or swelling when blood is drawn for laboratory tests. Rarely, infection can result from blood draws.
- It is possible that the participant's illness could worsen during the study. This could be related or unrelated to the study. Individuals with Major Depressive Disorder are at risk for depression, suicidal ideation, and suicide attempts as part of their illness. If the participant's illness worsens to the point that the study doctor considers them a danger to themselves or others, they will be hospitalized. If the participant is hospitalized they will be withdrawn from the study. In the event of hospitalization, the participant or the participant's insurance company will be responsible for the associated costs.
- It is possible that treatment with creatine will not be effective for the participant's depression, and that study participation will therefore delay the start of effective treatment.
- The researchers will take precautions to safeguard the participant's confidentiality, but it is possible that a breach of confidentiality could occur. A Certificate of Confidentiality has been obtained for this study.
- The participants may experience gastrointestinal discomfort as a result of taking study medication. We recommend taking the study medication with food to reduce possible stomach discomfort.
- MRI/MRS scans do not use ionizing radiation like x-rays or CT scans. Instead, magnetic fields and radio waves are used to take the pictures. There are no known risks related to MRI scans – other than the risk of injury when metallic objects are brought into the scanning room by mistake. Serious injury can occur during an MRI scan to persons who have:
 - Cardiac (heart) pacemakers.
 - Metal clips on blood vessels (also called stents).
 - Artificial heart valves.
 - Artificial arms, hands, legs, etc.
 - Brain stimulator devices.
 - Implanted drug pumps.
 - Cochlear [6] implants.
 - Ocular [118] implants or known metal fragments in eyes.
 - Exposure to shrapnel or metal fillings
 - Other metallic surgical parts.
 - Orthodontic braces on the teeth.
 - Body jewelry or piercings that cannot be removed for the scan.

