Overall Analytic Strategy: The analyses proposed are generalized estimating equations (GEE) regression modeling, which will be used for our longitudinal data analyses with group comparison across treatment visits for the variables of metabolite levels, depression/anxiety symptoms, and cognitive tests. GEE allows robust estimations of standard errors and permits adjustment for time-varying covariates. We assume that measurements made closer in time are more correlated than those made farther apart. Thus, first-order autoregressive structure is assumed. For our repeated measurement data, GEE fits a population-averaged model with working correlation structure to statistically evaluate the time effect of creatine supplementation. We will control for age, other drug abuse, anxiety scores, and tissue partial volume effects in each GEE model. Sidak multiple comparison procedure will be employed to adjust for family wise error (FWE) rate. The Sidak tests make conservative controls of FWE, giving slightly smaller adjusted p-values than the Bonferroni correction.

Overall Power and Sample Size Calculations: For this pilot study, considering a 20% attrition rate, 95 participants will be recruited to achieve a sample size of 75. To determine the minimum effect that would likely be detected with a sample size of 75, a power analysis was performed. Effect for the power analysis was specified as average baseline (over two measures) HAM-D scores compared with average HAM-D scores during active treatment (over eight measures). A gradual onset of effect during active treatment is assumed, starting with an effect of 0 and ending with an effect of 0.5, resulting in an average effect during treatment of 0.25. The effect to be tested was treated as a linear combination of the separate measures (y^*), and a pattern of correlation of 0.5 was used. This generated a standard deviation [105] for y^* that will be different from the within-occasion SD for Y itself. Then the effect magnitude specified was divided by the $SD(y^*)$ to generate an "effective" or de facto effect size, which resulted in an effect size of 1.09 with a power of 0.87.

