Statistical Analysis for Specific Aim 3: Cognitive testing data with a repeated measures design will evaluate the cognitive improvement after 8 weeks of creatine supplementation, specifically in executive and working memory deficits, found in MA users. The relative improvements on WCST, Stroop and WMS-IV scores associated with creatine versus placebo will be tested conservatively with the assumption of independence among comparisons. Independent variables include a time variable of "visit" (baseline and 8 weeks of treatment), creatine" (placebo or creatine group), and an interaction term, "creatine \times visit", where a significant interaction will indicate significant differences between treatments. The depression effect will be

tested by stratifying depressed and non-depressed MA users. Power and Sample Size Calculations: Previous reports, meta-analysis, and our preliminary data suggest that the cognitive deficits of MA users have medium-to-large (0.5 to 0.8) effect size, especially in the episodic memory, compared to healthy subjects. Thus, the proposed sample size (n=76) will have enough power (> 80%) based on Cohen's guidelines with adjusted Sidak p-values of 0.0169. [137, 138]

ADMINISTRATIVE RESPONSIBILITIES

Resources:

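### The plan randomises 123 women 1:1, but its placebo arm of 47 and its sample-size calculation (95 recruited, 75–76 analysed) describe a trial of about 94–95, and 123 is never explained

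*Combined protocol and SAP*

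**What the plan says.** The combined protocol and SAP gives the size of the randomised trial in several places.

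- **Participant Selection Criteria:** "123 women will be randomly assigned in a 1:1 ratio to either creatine or placebo for eight weeks".
- **Design:** "123 participants will be randomly assigned in a 1:1 ratio to placebo or 5 grams of daily creatine treatment for eight weeks". The same paragraph adds a separate group: "We also plan to recruit 24 age-matched females (18-55" years of age, who serve as healthy controls.
- **Study Procedures, randomisation paragraph:** "47 (50%) will be randomized to placebo". The list is to be generated before recruitment starts.
- **Risks and Benefits to Study Participants:** "There is a 50% chance that the participant will be assigned to placebo".
- **Overall Power and Sample Size Calculations:** "considering a 20% attrition rate, 95 participants will be recruited to achieve a sample size of 75".
- **Statistical Analysis for Specific Aim 3:** the power statement rests on 76 women: "the proposed sample size (n=76) will have enough power (> 80"%).

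No section derives 123, connects it to the power calculation, or records an increase in the target or a revised attrition rate.

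**The concern.** Equal allocation of 123 women cannot put 47 on placebo, and a trial that recruits 95 cannot randomise 123. The differences are too large for rounding.

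The number randomised is a basic design figure. As written, a reader cannot tell whether about 94–95 or 123 women are planned, or whether about 76 or about 98 are expected to be evaluable. Three things depend on the answer:

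- **Justification of size.** Both power statements rest on 75 or 76 women. If 123 is the target, nothing in the plan explains why 28–29 more women are randomised than the calculation calls for.
- **The randomisation list.** It is prepared in advance and its length is not given. A list built for 94–95 would not cover 123. This is a reason to check, not a demonstrated fault.
- **The end of recruitment.** The blind is held until recruitment closes and the last participant finishes eight weeks. With two possible targets, nobody can later judge whether recruitment stopped as planned.

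**Working it through.** **Inputs**

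| Quantity | Value | Section |
|---|---|---|
| Randomised, 1:1 | 123 | Participant Selection Criteria; Design |
| Placebo arm | 47, stated as 50% | Study Procedures |
| Recruited | 95 | Overall Power and Sample Size Calculations |
| Attrition | 20% | same |
| Analysed | 75 | same |
| Sample size for Aim 3 | 76 | Statistical Analysis for Specific Aim 3 |
| Controls, additional | 24 | Design |

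**Step 1. Reproduce the plan's own recruitment figure.** Number to recruit = number analysed / (1 − attrition).

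- From 75: 75 / 0.80 = 93.75, rounded up to 94.
- From 76: 76 / 0.80 = 95 exactly.

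The stated 95 is therefore reproduced, to within one participant from 75 and exactly from 76.

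**Step 2. Compare the placebo arm with that figure.** Total = 47 / 0.50 = 94. At 20% attrition, 94 × 0.80 = 75.2 and 95 × 0.80 = 76. So 47, 95, 20% and 75–76 form one consistent set. The difference between 75 and 76 is minor.

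**Step 3. Put 123 against that set.**

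- Per arm at 1:1: 123 / 2 = 61.5, that is 61 or 62, not 47.
- Evaluable at 20% attrition: 123 × 0.80 = 98.4, about 98, not 75–76.
- Excess over the number recruited: 123 − 95 = 28, and 28 / 95 = 29.5%.
- Excess over twice the placebo arm: 123 − 94 = 29, and 29 / 94 = 30.9%.

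**Step 4. Try the explanations that might reconcile the figures.**

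- *Controls counted in the total.* 94 + 24 = 118 and 95 + 24 = 119, neither of which is 123. Working back, 123 − 24 = 99, which appears nowhere. The controls are in any case additional and not randomised.
- *Screening losses.* Both statements of 123 describe women being randomised, not screened or consented.
- *95 as completers.* The power section applies attrition to 95, so 95 is the number before losses.
- *Heavier attrition.* Going from 123 to 75 needs 1 − 75/123 = 39.0%; to 76 it needs 1 − 76/123 = 38.2%. The only rate stated is 20%.
- *Allowance for omitted scans or cognitive tests.* The footnotes to Table 2A permit both omissions, but no section links them to the sample size.

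None of these yields 123 from the figures given.

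**The case against.** The contradiction itself is hard to dispute; the fair objections concern its reading and its weight.

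- **The allocation ratio is not in doubt.** Every section that mentions it says 1:1 or 50%. Expressing 47 as a share of 123 (38.2%) only restates the mismatch in counts. This stands: the conflict lies in the numbers, not in the intended ratio.
- **The power section says recruited, not randomised.** Correct, so the exact comparison is 123 randomised against 95 recruited, or against the 94 implied by the placebo arm. It does not help the plan, since recruitment cannot be smaller than randomisation.
- **The pattern looks like a target that was raised while the supporting text was left alone.** That is plausible, but no section says so. If it happened, the placebo count and both power statements are out of date and still presented as current.
- **A larger trial would do no harm to power.** If 123 is right, about 98 evaluable women exceeds the 75–76 assumed, and neither the planned GEE analysis nor the hypotheses change. This stands, and it is why no claim of bias or lost power is made. It does not supply a reason for the larger number.
- **The 38–39% attrition is only a back-calculation.** Agreed. It serves to show that the stated 20% cannot connect 123 to 75–76, and no motive should be read into it.

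**Conclusion.** The concern holds. Within one document, the number randomised (123) is incompatible with the placebo arm (47), the number recruited (95) and the evaluable number (75–76 at 20% attrition). The gap is 28–29 women, about 30%; per arm it is 61 or 62 against 47; in evaluable participants it is about 98 against 75–76.

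The result uses only printed figures and simple arithmetic, with the stated 20% applied as a proportion of those enrolled. It does not establish which total is right, because the documents do not settle that, and it shows no bias. It must nevertheless be corrected, because the trial's stated size and its only stated rationale cannot both be true.

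**What to change.** Choose one number randomised and carry it through the Participant Selection Criteria, Design, Study Procedures, Overall Power and Sample Size Calculations and the Aim 3 analysis, with matching arm sizes, one attrition rate and the resulting evaluable number.

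- **If 123 is intended:** replace the placebo count with 61 or 62. Give either about 98 evaluable at 20% attrition, or a different attrition rate with its reason. Say why the target exceeds 95, and restate both power statements at the new number.
- **If 94–95 is intended:** correct 123 in the two places where it appears, and settle 75 against 76.
- **In either case:** confirm that the pre-generated randomisation list covers the full stated number.

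The cost is modest but goes beyond a text edit. Under the Data Safety Monitoring Plan (Reporting Protocol Changes), changes go to the IRB and FDA for approval and need the agreement of the NIDA program officer. If 123 is the target, the HAM-D power figure has to be recalculated rather than rescaled: read as a two-arm comparison of 75 women in total, at an assumed two-sided 0.05 (that section states no alpha), an effect size of 1.09 gives power of about 0.997, not the stated 0.87. No enrolment beyond the stated 123 is needed.

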A key phosphorus (^{31}P) magnetic resonance spectroscopy (MRS) finding from our ongoing research is significantly decreased phosphocreatine (PCr) in MA users, an effect that is greater in females than males [22]. Notably, in rats creatine administration significantly increases the brain content of both creatine and PCr [23]. In human studies, the increase in brain total creatine (PCr + creatine) after oral creatine supplementation is a finding replicated by three independent groups, including ours [24-26].

The importance of assessing glutamatergic systems in MA users is attested to by the fact that more than 80% of neurons are excitatory, and that greater than 90% of synapses release glutamate [27]. Of relevance to our preliminary proton (^1H) MRS findings showing an association between the glutamine/glutamate ratio and lifetime MA use, it has been reported that PCr stimulates synaptic glutamate uptake thereby reducing extracellular glutamate [28], which is another potential neuroprotective mechanism of creatine. Importantly, depletion of PCr and ATP is an early event in glutamate excitotoxic neurodegeneration [29, 30]. Therefore, based on our finding of decreased PCr in MA users, it is of interest that a recent ^1H -MRS investigation reported that glutamate levels in frontal white matter are significantly higher in abstinent MA users versus control subjects [31], which is compatible with MA-induced neurotoxicity.

Female Methamphetamine Initiation, Addiction and Relapse are Influenced by Depression:

The prevalence of pre-morbid depressive disorders in MA users is high, with a majority reporting a significant lifetime history of depression [1, 3, 70]. For example in one study [70], MA users had a 62% rate of depression and a 23% rate of suicidality prior to MA use. After MA was initiated, the rate of depression increased to 79% [70]. Studies reporting gender differences in psychopathology have found that MA use is associated with depression in both adult [60] and

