The lack of safe and effective pharmacological treatments for MA use disorders is a critical barrier to improved treatment outcomes. This proposal builds on the published translational findings of reduced PCr[22] and NAA [34, 124] levels in MA use disorders, and the clinical and neuroimaging findings from our preliminary study of creatine for MA-using females. At the same time, it follows the recommendation of experts – including NIDA Director [name] and the eminent substance abuse researcher [name] – that strategies outside the brain dopamine reward system be adopted [56, 125, 126]. Achievement of these *Specific Aims* would validate the notion of neuroprotective agents as potential treatments for MA addiction [15], and in particular those which are also capable of improving mood/anxiety and cognitive symptoms. Incorporating pre- and post-treatment imaging into studies of substance misuse can facilitate identification of the neural predictors and correlates of effective MA treatment [127]. Because the effects of drug use on brain function impede patients' ability to benefit from treatment, studies of drug-related alterations in neurobiology utilizing translational study designs are warranted [127]. Thus, we propose an 8-week, randomized, placebo-controlled trial of creatine for females with MA addiction.

Specific Aims for this proposal are: **1. To define the extent of restoration in bioenergetic dysfunction and neuronal viability following creatine supplementation in female MA users.** We hypothesize that creatine will be superior to placebo in the degree of improvement in PCr and NAA levels, measured with ^{31}P -MRS and ^1H -MRS. Changes to the glutamine/glutamate ratio and GABA will be assessed in an exploratory manner. **2. To assess creatine's antidepressant/anxiolytic effect in female MA users.** We hypothesize that creatine will be

superior to placebo in reducing Hamilton Depression Rating Scale (HAMD) and Beck Anxiety Inventory [97] scores. 3. To Measure the Degree of Cognitive Improvement Associated with Creatine in Female MA Users. We hypothesize that creatine will be associated with greater improvement in cognitive function tests, compared with placebo. In addition to these Specific Aims, we will examine urine drug testing results in an exploratory manner, to determine whether creatine vs. placebo is associated with a greater number of MA-free tests

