 - i. Reporting to the University of Utah Institutional Review Board. If a protocol violation/deviation meets one or more of the following criteria, the PI will submit the violation/deviation via ERICA within 10 working days from the time the investigator learns of the event.
 - Intended to eliminate apparent immediate hazard to a research participant; or
 - Harmful (caused possible harm to participants or others, or places them at increased risk of harm – including physical, psychological, economic, or social harm, such as breach of confidentiality); or
 - Possible serious or continued noncompliance (such as a deviation that has happened previously and is now being repeated).
 - ii. Reporting to the Food and Drug Administration. Protocol violations/deviations will be summarized in the annual IND report.

Trial Stopping Rules

In our open-label study of 5 grams of daily creatine for 8-weeks, there were no unanticipated problems or SAEs reported. Considering this is a feasibility study of double-blind, placebo-controlled creatine at the same dose as our open-label study, and the open-label creatine was well tolerated with a low side effect profile, we have not adopted rules for stopping the study. We have, however, developed criteria for early termination of participants and the criteria are listed below:

- Suicide attempt
- Psychiatric hospitalization

- Onset of bipolar disorder or psychotic disorder
- Positive pregnancy test
- Incarceration
- Inability to comply with the study protocol

IMAGING METHODS AND DATA ANALYSIS

1. Neuroimaging Protocol

i. Magnetic Resonance Imaging (Siemens Trio 3T MRI system)

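### Table 1 does not exclude women already taking creatine supplements, and nothing in the available text asks participants to avoid non-study creatine during the trial

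*Combined protocol and SAP*

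**What the plan says.** **Eligibility.** Table 1 lists ten exclusions, and the only one that mentions creatine is "History of hypersensitivity reaction to creatine". The only rule on prior treatment is an inclusion criterion about psychotropics: "If taking a psychotropic medication for depressed mood, regimen must be stable for ≥ 4 weeks prior to randomization".

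**Washout.** Study Procedures, in the paragraph on randomization, states: "There is no 'washout period' for any participant in this study". The same sentence goes on to say that "participants randomized to placebo will continue treatment with a psychotropic medication throughout their time in the study".

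**Why creatine intake matters.** The background section on brain PCr states that "the increase in brain total creatine (PCr + creatine) after oral creatine supplementation is a finding replicated by three independent groups". Aim 1 then tests whether creatine improves PCr and NAA more than placebo does.

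**What is recorded.** Table 2A schedules Concomitant Medications at screening and in every week to week 11, and a Food Frequency Questionnaire at screening and week 9. Neither is tied to eligibility, to a restriction or to the analysis. The covariates in the Overall Analytic Strategy are age, other drug abuse, anxiety scores and tissue partial volume.

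**Earlier creatine work.** Trial Stopping Rules begins: "In our open-label study of 5 grams of daily creatine for 8-weeks, there were no unanticipated problems or SAEs reported". The summary of significance refers to "clinical and neuroimaging findings from our preliminary study of creatine for MA-using females".

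**The concern.** The study product is an oral supplement, and the reference list itself describes creatine as a dietary supplement. Participants are also told what the product is: the risk section explains that those on placebo will not receive creatine. Use outside the trial, before or during it, is therefore foreseeable, yet a site following Table 1 as printed would have no ground to exclude a current user.

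What is at stake is the contrast between arms. By the protocol's own premise, a woman who already supplements may enter with raised brain creatine and have less room to rise on study creatine. A woman on placebo who begins taking creatine receives something close to the active treatment. Both make creatine look less different from placebo. PCr in Aim 1 is the most directly exposed outcome. The depression, anxiety and cognitive outcomes are exposed only so far as creatine affects them.

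**Working it through.** The plan gives no figure on this point, so there is none to reproduce. The check has two parts: who dilutes the comparison, and by how much for an assumed share of users.

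**1. Who dilutes a change contrast.** Aim 1 is worded as degree of improvement, and the Aim 3 analysis spells out a treatment-by-visit interaction, so the comparison is of change. Let Δ be the true creatine effect on change and δ the change on placebo.

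- Creatine arm, with a share p already supplementing and gaining nothing further: mean change = δ + (1-p)Δ.
- Placebo arm, with a share p supplementing steadily: they start raised and stay raised, so mean change = δ.
- Contrast = (1-p)Δ. The loss comes from the creatine arm alone.
- If instead a share s of the placebo arm starts creatine during the trial and gets the full effect, the placebo mean is δ + sΔ and the contrast is (1-s)Δ. With both, it is (1-p-s)Δ.

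**2. Sample size.** For a fixed SD, the required n is proportional to 1/effect², so it rises by 1/(1-p)^2. The counts use the 123 women to be randomised. The values of p are assumptions.

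| Assumed p | 123 × p | Effect retained | 1/(1-p)^2 | Extra sample |
|---|---|---|---|---|
| 2% | 2.5 | 0.98 | 1/0.9604 = 1.04 | 4% |
| 5% | 6.2 | 0.95 | 1/0.9025 = 1.11 | 11% |
| 10% | 12.3 | 0.90 | 1/0.81 = 1.23 | 23% |

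**3. The same loss as power.** This takes the power section's evaluable 75 (37.5 per arm) and its power of 0.87 as a starting point only, without endorsing how that power was derived. At two-sided 5%, the standardised effect giving 0.87 is (1.960 + 1.126) × √(2/37.5) = 0.713.

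- p = 5%: effect 0.713 × 0.95 = 0.677, power 0.83. Evaluable n to restore 0.87 is 75 × 1.108 = 83.
- p = 10%: effect 0.713 × 0.90 = 0.641, power 0.79. Evaluable n to restore 0.87 is 75 × 1.235 = 93.

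**4. Does anything else close the gap?** Setting Table 1, Study Procedures, Table 2A and the analysis section side by side, none excludes, restricts or adjusts for non-study creatine. The two records that could reveal it have no stated consequence.

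**The case against.** **The washout sentence is not about creatine.** A reader might infer that the plan deliberately admits creatine users without washout. Read whole, the sentence moves straight to continued psychotropic treatment and matches the stable-regimen criterion, so that inference is not supported. What remains is an omission in Table 1, which stands without the sentence.

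**Existing users in both arms do not both dilute.** One might suppose that a placebo participant who already supplements also pulls the result toward zero. In a comparison of change she does not, as step 1 shows. Only creatine-arm users and women who start during the trial do. Randomisation also means that pre-existing use does not inflate type I error; the cost is power.

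**Prevalence may be negligible.** Recruitment is mainly through substance-use assessment services, and nothing in the documents suggests that creatine use is common there. This objection stands and limits the weight of the point.

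**An instruction may exist elsewhere.** The consent pages were not available and could ask women to avoid supplements. That would deal with use during the trial, but an eligibility rule still belongs in Table 1.

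**Users could be found afterwards.** Concomitant Medications, the Food Frequency Questionnaire and, in scanned women, baseline PCr could support a sensitivity analysis. That is a fair partial remedy, but none is planned.

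**Former open-label participants.** It is tempting to add that women from the team's open-label study could re-enter, recognise the product and weaken the blind. The passage giving dose and duration states no population, and the passage on methamphetamine-using females states neither dose nor open-label design; that they are one study is an inference. No text describes re-recruiting those women, the appearance and taste of the products are not described, and the Research Pharmacy dispenses blinded. The documents do not support treating this as a demonstrated problem.

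**Conclusion.** The gap is real but minor. As printed, the plan allows women already taking the study product to be randomised, and the available text does not ask anyone to avoid it during treatment. The likely effect is a smaller creatine-placebo contrast and some lost power, chiefly for PCr in Aim 1.

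The size cannot be stated from the documents. The 4%, 11% and 23% rest on three assumptions: a share of users of 2%, 5% or 10%; no contrast at all from those women, which is the unfavourable extreme; and an unchanged SD. Partial response in existing users would make the loss smaller. The documents do not show that any such woman was or would be enrolled.

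**What to change.** - Add one exclusion to Table 1: use of a creatine-containing supplement within an interval before the baseline scan, to be defined by the sponsor, or unwillingness to avoid such supplements until the week-9 scan.
- Ask about supplements explicitly at the Concomitant Medications check, which is already made at screening and every study week.
- Reword the washout sentence in Study Procedures so that it clearly refers to psychotropic medication.
- As an optional precaution, exclude participants of the team's earlier open-label creatine study. This is reasonable, but the documents do not show a need for it.

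The cost is a few lines of text, one question at an existing visit and probably a very small loss of eligible women.
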